### 14.2.3 Collection of Ablation Procedure Data for Post-Analysis (non-SOC)

At the completion of the study ablation procedure, two back-up copies of the CARTO®3 and generator system log files will be made. One copy should be kept at the site within the investigator site or patient binders, and one fully anonymized copy will be provided to/collected by the Sponsor.

#### 14.2.3.1 Data Collection during Study Ablation Procedure

The following information will be collected during the procedure, including but not limited to:  
**Technical parameters are collected via CARTO® datafiles and generator files, including but not limited to:**

- Number of PFA applications
- Energy delivered
- PFA application time
- Ablation settings
- Ablation lesion information will be collected in the CARTO®3 system and IRE Generator

**Other procedural parameters are collected via Electronic Data Capture (EDC), including but not limited to:**

- Use of a non-study catheter for PVI
- Number of PFA applications per target PV
- Number of RF applications required with a non study catheter
- PVI confirmed with Lasso® or PentaRay or Circular IRE Catheter
- PV acute reconnection (early or dormant)
- Procedure time (from first femoral puncture to last catheter out)
- Mapping time (start mapping - end mapping)
- Total fluoroscopy time
- Total study catheter LA dwell time (from first study catheter insertion in LA until study catheter removal from LA)
- ECG data
- Total fluid delivered via study catheter
- Total fluid delivered via intravenous line (if captured)
- Fluid output (if captured)
- Device deficiency information (if applicable)
- Procedural medication (paralytics)
- Anesthesia type

#### 14.2.4 Pre-Discharge Assessments

Prior to hospital discharge, the following assessments should be performed:

- Medication regimen (Cardiac, anti-coagulation, PPIs)
- Imaging assessment of pericardial fluid presence
- AEs events
- ECG in case standard of care

- **For Wave I subjects (non-SOC):**

- Cerebral MRI, neurological exam and neurological evaluation using the NIH stroke scale within 72-hours post procedure, preferable prior to discharge. A certified/qualified physician expert must perform neurologic exams at pre- and post-ablation and possibly at other follow-up visits, pending previous findings of micro-emboli/neurologic deficits. For procedures on Friday a window of a maximum of 96 hours is justified. Note: Patient questionnaires will only be used in countries with validated languages
- Endoscopy to check for any esophageal lesions and/or damage will be performed preferable prior to discharge and no later than 72 hours after procedure (for procedures on Friday a window of a maximum of 96 hours is justified). Endoscopy images will be transmitted to a central reader.

#### 14.2.5 Repeat Ablation Procedures

Repeat procedures may be performed at the discretion of the investigator. It is highly recommended to collect arrhythmia documentation (in example documented recurrences) before performing a repeat procedure.

Repeat procedures during the blanking period (90 days post index procedure) must be conducted with the investigational device, with or without focal touch-up, if the arrhythmia is due to PV triggers. If the arrhythmia is due to non-PV triggers and the subject is treated with a commercially available ablation catheter and generator, the subject will be excluded from the long term effectiveness cohort.

Repeat procedures performed after the blanking period may be managed per investigator discretion using a commercially available ablation catheter and generator.

The follow-up schedule will remain based on the initial ablation procedure.

#### 14.3 Post-Ablation Follow-up Schedule

The subject will be required to complete follow-up visits through 12 months post initial ablation procedure. Follow-up will be done at 7 days (phone call or clinic visit), 1, 3, 6 and 12 months (clinic visit).

**At 7-day follow-up visit, the following assessments will be performed:**

Discharged subjects will receive a telephone call or have a clinic visit at 7 days (7D, day 7-9) post ablation procedure to assess any occurrence of Primary Adverse Events and any change in medication regimen;

Follow-up visits should be scheduled according to the following timeframes: 1 month (1M 23-37), 3 months (3M, day 76-104), 6 months (6M, day 166-194) and 12 months (12M, day 335-379). Follow-up visit schedule should be based on the date of the index study ablation procedure and will not reset if subject undergoes a repeat AF ablation procedure.

**At 1, 3, 6 and, 12-month follow-up visits, the following assessments will be performed:**

- Medical evaluation:
  - AEs
  - Cardiac and Anti-coagulation medication regimen
  - Cardiac related hospitalization and cardioversions
  - 12 Lead-ECG (if completed per standard of care)

- **Atrial arrhythmia monitoring as from month 3 (non-SOC)**
  - Remote Monitoring:  
Subjects will be provided with a remote monitoring device at the 3M FU visit and asked to record and transmit a minimum of 1 transmission ( $\geq 30$  seconds) every week through the end of the month 5 of FU. Starting at month 6 of FU, subjects will be asked to record and transmit a minimum of 1 transmission ( $\geq 30$  seconds) every month until the effectiveness evaluation period is completed (12 months post index procedure). Subjects will also be asked to transmit any symptom-triggered episode that occurs from the time they receive the remote monitoring device through the 12M FU visit. A core lab might be used to evaluate and assess the remote monitoring tracings.  
  
Remote monitoring will be conducted as follows:
    - Distribution and start by month 3
    - <6M: Weekly transmission of at least 1 scheduled recording
    - $\geq 6M$ : Monthly transmission of at least 1 scheduled recording
    - Conduct and transmit recording whenever symptoms are present
  - 24 Hour Holter:  
Holter monitor will be used at each follow-up visit to monitor the subjects' heart rhythm for 24 hours continuously. Following the 24h Holter, subjects will be contacted by the site to verify if symptoms are experienced during 24h Holter.
- Quality of life via the **Atrial Fibrillation Effect on Quality-of-Life (AFEQT™)** questionnaire (non-SOC), at Month 3, 6 and 12. Note: Patient questionnaires will only be used in countries with validated languages.
- **Cardiac CT/MRA**
  - **Wave I subjects:** is required to be performed at the 3M FU visit (non-SOC) or any other point in time when subject presents with symptoms of PV stenosis.
  - **Wave II subjects:** is only required to be performed if subject presents with symptoms of PV stenosis.
- **Wave I subjects only: Cerebral MRI, Neurological Exam and Neurological Evaluation using the MMSE, NIHSS and mRS (non-SOC)** are required to be performed if any neurological symptoms and/or cerebral ischemic lesions were identified at a prior evaluation. Note: Patient questionnaires will only be used in countries with validated languages.

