### 14.7 Schedule of Events Table

Table 5 displays the required schedule for subject treatments and evaluations.

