**Table 5: Summary of Subject Visits and Assessments**

Assessments	Pre-Procedure	Pre-Discharge	Follow-up					UNS
			7 Day	1 Month	3 Month	6 Month	12 Month	
Study Day			D7	D30	D90	D180	D365	
Visit window			D7-D9	D23-D37	D76-D104	D166-D194	D335-D379	
Clinic visit	●	●	(●)	●	●	●	●	● 
Phone call			●					
Patient Informed Consent 	●							
Demographics	●							
Medical History 	●							
Pregnancy test 	●							
LA and LVEF assessment 	●							
Left atrial thrombus detection 	●							
Pericardial fluid assessment		●						
12 Lead ECG 	●	●		●	●	●	●	● 
Atrial Arrhythmia monitoring (Remote) 					●	●	●	● 
Atrial Arrhythmia monitoring (24 hour Holter) 					●	●	●	● 
Repeat ablations 			●	●	●	●	●	● 
Concomitant Medication 		●	●	●	●	●	●	● 
Device Deficiencies		●						
Adverse Events 	●	●	●	●	●	●	●	● 
AFEQT 	●				●	●	●	
Cardiac CT/MRA	●				● 			
Wave I subjects ONLY additional assessments								
Endoscopy		● 						
Cerebral MRI 	● 	● 		● 	● 	● 	● 	● 
Neurological Exam 	● 	● 		● 	● 	● 	● 	● 
NIH Stroke Scale 	● 	● 		● 	● 	● 	● 	● 
mRS	● 			●	● 	● 	● 	● 
MMSE 	● 			●	● 	● 	● 	● 

1. Procedure must be done within 60 days of consent.
2. Medical history-including but not limited to arrhythmia, AAD therapy failure, heart disease (NYHA), vital signs, CHA2DS2score and thromboembolic events.
3. In all women of childbearing age and potential. To be completed within 72-hours prior to ablation procedure.
4. Imaging within 6 months prior to procedure to assess the LA and LVEF, in case the imaging assessment is older than 6 months, LA/LVEF dimensions shall be re-measured during the index procedure prior to insertion of the study catheter.

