5. Performed the day before procedure or day of ablation procedure to rule out the presence of atrial thrombus using one of the following modalities TEE, ICE, CT, MRI.
6. If Standard of care assessment (For pre-procedure, can be performed before ICF signature)
7. Arrhythmia monitoring via remote monitoring once per week as from 3-month follow-up visit to the end of 5-month follow-up and monthly as of 6-month follow-up visit and whenever subject feels symptoms.
8. Arrhythmia monitoring via 24H Holter, site to contact subject and verify if any symptoms experienced during the Holter monitoring.
9. Information on any repeat ablation after the index procedure will be collected
10. Concomitant medication: only cardiac (i.e. anti-arrhythmia drugs, anticoagulation regimen) & index procedure related (i.e. adenosine, pain medication)
11. AEs must be collected from the time the subject signs the informed consent onward.
12. To be completed within 6 months prior to ablation procedure, For Wave I subjects: CT-MRA to be repeated at 3M FU. For Wave I and Wave II subjects, CT-MRA to be repeated post procedure in case subject presents with PV stenosis symptoms.
13. Endoscopy preferable prior to discharge and no later than 72-hours after procedure. For procedures on Friday a window of a maximum of 96 hours is justified.
14. If observations are noted on the post-procedure MRI, the subject must have follow-up MRI at the next follow-up visit(s) until observations are resolved.
15. A certified/qualified physician expert must perform neurologic exams at pre-and post-ablation and possibly at other follow-up visits, pending previous findings of micro-emboli/neurologic deficits.
16. To be completed within 72-hours pre-procedure. For procedures on Monday a window of a maximum of 96 hours is justified.
17. To be completed within 72-hours post-procedure. For procedures on Friday a window of a maximum of 96 hours is justified.
18. Full neurological follow up to be undertaken if neurologic symptoms and/or cerebral ischemic lesions identified in a prior evaluation.
19. If subject returns for a potential study related cardiovascular or neurological visit outside of the protocol-defined visit schedule as deemed required per investigators discretion.
20. Patient questionnaires will only be used in countries with validated languages.

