7.6.4 Neurological Evaluations

The following analyses of neurological evaluations will be conducted using the mITT analysis set and summarized descriptively. In addition to the timepoints explicitly stated below, subjects will undergo full neurological follow-up only if neurologic symptoms and/or cerebral ischemic lesions are identified in a prior evaluation; results for these additional neurological evaluations will be summarized descriptively. Neurological evaluation questionnaires, including Mini Mental State Examination (MMSE), National Institute of Health Stroke Scale (NIHSS), and Modified Rankin Scale (mRS) will only be used in countries with validated languages. Only subjects in countries where the neurological evaluation questionnaires are applied will be included in the associated analyses.

- **Neurological Exam:** The occurrence of new or worsening neurological deficits post-ablation compared to pre-ablation will be summarized descriptively by timepoint.
- **Cerebral Emboli:** The frequency, anatomical location (side and area), and size (diameter and volume) of asymptomatic and symptomatic cerebral emboli observed pre-ablation and new emboli observed post-ablation as determined by Magnetic Resonance Imaging (MRI) evaluations assessed by a central core lab will be summarized descriptively by timepoint.
- **Mini Mental State Examination (MMSE):** The MMSE includes tests of registration, orientation (time and place), recall, attention and calculation, and language and praxis (naming, repetition, comprehension, reading, writing, and drawing)². The total score ranges from 0 to 30, with lower scores indicating greater cognitive impairment. MMSE scores pre-ablation and change from pre-ablation at the 1-month follow-up will be summarized descriptively. MMSE scores will also be plotted by timepoint.
- **National Institute of Health Stroke Scale (NIHSS):** The NIHSS is a 15-item quantitative measure of stroke-related neurologic deficit on the levels of consciousness, language, neglect, visual-field loss, extraocular movement, motor strength, ataxia, dysarthria, and sensory loss³. The total score ranges from 0 to 42, with scores equal to 0 indicating no stroke symptoms, score ranging 1-4 indicating minor stroke, ranging 5-15 a medium stroke, 16-20 a moderate to severe stroke, and a range 21-42 a severe stroke. NIHSS scores pre-ablation and post-ablation prior to discharge will be summarized descriptively and plotted by timepoint.

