- **Modified Rankin Scale (mRS):** The mRS is a disability scale with possible scores ranging from 0 to 6, where 0 indicates no symptoms and 6 indicates subject expiration⁴. mRS scores pre-ablation and change from pre-ablation at the 1-month follow-up will be summarized descriptively. mRS scores will also be plotted by timepoint.

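### Protocol 14.3 ties the 1-month MMSE and mRS in Wave I to a prior symptom or lesion, while Tables 1 and 5 schedule them without that condition and the Wave I SAP analyses them in the mITT set

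*Protocol*

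**What the plan says.** Four parts of the plan bear on the 1-month MMSE and mRS in Wave I.

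- **Protocol 14.3.** Under the lead-in "At 1, 3, 6 and, 12-month follow-up visits, the following assessments will be performed", the Wave I item groups cerebral MRI, neurological exam, MMSE, NIHSS and mRS and says that they "are required to be performed if any neurological symptoms and/or cerebral ischemic lesions were identified at a prior evaluation". It makes no exception for month 1.
- **Protocol Tables 1 and 5.** In the block "Wave I subjects ONLY additional assessments", the 1-month entries for MRI, neurological exam and NIHSS carry footnote 18: "Full neurological follow up to be undertaken if neurologic symptoms and/or cerebral ischemic lesions identified in a prior evaluation". The 1-month entries for mRS and MMSE carry no footnote; their 3, 6 and 12-month entries carry footnote 18. Section 14.7 states: "Table 5 displays the required schedule for subject treatments and evaluations".
- **Protocol 14.2.4.** Before discharge the Wave I items are "Cerebral MRI, neurological exam and neurological evaluation using the NIH stroke scale within 72-hours post procedure" and endoscopy. MMSE and mRS are not listed there or in the tables' pre-discharge column.
- **Wave I SAP 7.6.4.** In the mITT set, "MMSE scores pre-ablation and change from pre-ablation at the 1-month follow-up will be summarized descriptively", and likewise "mRS scores pre-ablation and change from pre-ablation at the 1-month follow-up will be summarized descriptively". The section presents symptom- or lesion-driven follow-up as additional to the timepoints it names.

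The endpoint list in Protocol 8.2.3 (and the protocol summary) asks for MMSE, NIHSS and mRS at baseline, post-ablation and during follow-up, with a bracket that refers to lesions found at a prior evaluation.

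**The concern.** Wave I is the safety-characterisation phase, and neurological assessment is one of the things that sets it apart from Wave II. The SAP's 1-month change in MMSE and mRS is meant to describe the mITT set. A site that works from 14.3 would obtain these scores in subjects selected because a symptom or lesion had already been seen. The resulting summary would carry the mITT label but describe a selected few. If some sites worked from the table and others from 14.3, the mean would mix complete and selected sites.

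Nothing earlier fills the gap: month 1 is the first scheduled post-ablation MMSE and mRS. I found no rule on whether text or table takes precedence. Protocol 17 requires all instructions to be followed and counts a missed test as a deviation, so a site following 14.3 would appear to deviate from Table 5.

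**Working it through.** **1. Passages side by side (1-month visit, Wave I).**

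| Item | Protocol 14.3 | Tables 1 and 5 | Wave I SAP 7.6.4 |
|---|---|---|---|
| MRI, neurological exam, NIHSS | after prior symptom or lesion | after prior symptom or lesion (footnote 18) | month 1 not named individually |
| MMSE, mRS | after prior symptom or lesion | no condition | change from pre-ablation at 1 month |

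The conflict is confined to the second row at month 1. From month 3, text and tables agree.

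**2. The plan's own Wave I figure.** Protocol 20.2 and Wave I SAP section 6 give a probability above 90% of at least one primary adverse event, with 35 subjects having the catheter inserted and a rate of 7%. Check: 1 − 0.93^35 = 0.921. This agrees. The documents give no figure for the number of subjects behind the 1-month MMSE or mRS change.

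**3. Illustration of the 14.3 reading.** Inputs:
- n = 35 with the catheter inserted (Protocol 20.2, SAP section 6), since the mITT set requires insertion. Enrollment is up to 40.
- p = 2% to 15%, the range for asymptomatic cerebral emboli after AF ablation in Protocol 6.4.1.
- Assumption: a new silent embolus is the only trigger. This understates the count, because symptoms also trigger and a baseline MRI finding may count as prior.

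Number measured ~ Binomial(n, p); expected number = n × p; chance of none = (1 − p)^n.

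| n | p | Expected measured | 5th to 95th percentile | Chance of none |
|---|---|---|---|---|
| 35 | 2% | 35 × 0.02 = 0.7 | 0 to 2 | 0.98^35 = 0.49 |
| 35 | 15% | 35 × 0.15 = 5.25 | 2 to 9 | 0.85^35 = 0.003 |
| 40 | 2% | 40 × 0.02 = 0.8 | 0 to 2 | 0.98^40 = 0.45 |
| 40 | 15% | 40 × 0.15 = 6.0 | 3 to 10 | 0.85^40 = 0.002 |

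Protocol 6.4.1 also says that data on cerebral lesions with this energy source are limited. As a stress value not taken from the documents, p = 30% gives 35 × 0.30 = 10.5.

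**4. The table reading.** About 35 subjects, less those discontinued (exempt from the Wave I assessments under Protocol 10.3), those missing, and those in countries without a validated version.

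Under the illustration, 85% to 98% of the 35 would have no required 1-month MMSE or mRS.

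**The case against.** The strongest reply is that the plan already shows what is meant. Both tables agree, 14.7 calls Table 5 the required schedule, and SAP 7.6.4 separates its named timepoints from conditional follow-up. Section 14.3 says when the assessments are required; it does not say that they are otherwise omitted, whereas the neighbouring Wave II CT/MRA item does restrict itself explicitly. It can be read as describing the full bundle that footnote 18 covers. The bracket in 8.2.3 may attach to follow-up alone and leave the post-ablation score unconditional. All of this stands as evidence of intent. It does not remove the conflict, because 14.3 names MMSE and mRS, covers month 1 and makes no exception.

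Three stronger readings are tempting, and the documents do not support them.

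- A reader might infer that the 1-month change will rest on one to six lesion-positive patients, or that there is a 45% chance it cannot be computed. Those figures use 40 subjects and count only new silent emboli. Symptoms also trigger assessment, a baseline lesion may do so, and the shortfall arises only where sites follow 14.3.
- A reader might infer that the SAP is wrong to apply the validated-language limit to mRS, because the tables put footnote 20 on NIHSS and MMSE but not on mRS. Protocol 8.1.1, 14.2.1 and 14.3 each attach the language note to text that names mRS, so the SAP matches them. This is a second inconsistency to reconcile, not an error on the SAP's side alone.
- A reader might infer that the neurological status of lesion-free subjects would be unknown. Ablated Wave I subjects still have the post-procedure MRI, neurological exam and NIHSS (the last subject to the language limit), and stroke and TIA are primary adverse events in everyone.

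It is also fair to say that a small denominator would be visible: Wave I SAP 7.1 reports the number of observations with data. It does not report the number missing, which Protocol 20.4.1 does, and SAP 7.4.3 rules out imputation. The reader would see a small n without the number expected.

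**Conclusion.** The point holds as an inconsistency that should be corrected. Read as written for month 1, Protocol 14.3 requires MMSE and mRS only after a prior symptom or lesion; Tables 1 and 5 carry no such condition, and SAP 7.6.4 depends on the table version. At sites following 14.3, a subject without symptoms or lesions would have no required post-ablation MMSE or mRS.

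The size cannot be fixed from the documents. The figure of about 0.7 to 5 of 35 is an illustration that rests on the protocol's general AF-ablation range, on silent emboli as the sole trigger, and on every site following 14.3. Relaxing any of these would be expected to raise it. The consequence is selection and a small denominator in a descriptive additional endpoint. Wave I tests no hypothesis, so no power or type I error figure is affected.

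**What to change.** 1. Reconcile Protocol 14.3 with Tables 1 and 5 and Wave I SAP 7.6.4, so that the 1-month MMSE and mRS are collected in all ablated Wave I subjects (subject to the language limit). The symptom-or-lesion condition would then apply to the 1-month MRI, neurological exam and NIHSS, and to all items from month 3.
2. State in 8.2.3 and the protocol summary that the bracket about prior lesions does not apply to the 1-month MMSE and mRS.
3. In SAP 7.6.4, report the number assessed out of the number expected for the 1-month change in each score. This remains useful if the 1-month visits are already complete, because it shows which rule was followed in practice.
4. Reconcile whether the validated-language limit covers mRS between the table footnotes, Protocol 8.1.1, 14.2.1 and 14.3, and SAP 7.6.4.

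Showing the 1-month change by post-ablation lesion status would be an optional extra; the plan does not promise that comparison.

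The cost is wording in the protocol and SAP. The assessments already stand in Table 5 at an existing clinic visit, so nothing is added to that schedule.

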#### 14.4 Early Termination Visit

If early termination of the study is required due to safety concerns, each site will undergo a monitoring visit to conclude any outstanding issues, collect all outstanding CRF information, verify device accountability, and discuss any other items relevant to the conclusion of the study. Any enrolled subjects will continue to be followed per the study protocol requirements. In case of early termination due to safety concerns, reporting to EC and CA may be required per local regulations.

#### 14.5 Unscheduled Visit

If a subject returns for a potential study related cardiovascular or neurological visit outside of the protocol-defined visit schedule provided in table 5, the visit will be considered "unscheduled" (UNS). An investigator may request an unscheduled visit in the presence of a new or worsened cardiovascular condition or neurological deficit. If the unscheduled visit is

for a repeat ablation procedure, the protocol follow-up schedule is based on the index ablation procedure. For all unscheduled visits, an unscheduled visit eCRF must be completed and the subject must also return for their next scheduled study visit per clinical investigational plan.

